Clinical Study Protocol

An Open-Label, Parallel-Group, Single-Center Phase 1 Clinical Study to Evaluate the Pharmacokinetics of a Single Oral Dose of Mavacamten in Healthy Adult Chinese Subjects

Investigational Drug	Mavacamten Capsules
Protocol No.	LB2001-101
Phase of Development	1
Registration Category	Chemical Drug Category 1
Proposed Indication	Obstructive Hypertrophic Cardiomyopathy
Version and Date	1.0/ 30 Apr 2021
Sponsor	Shanghai LianBio Development Co., Ltd.
Address	[name]

Statement of Confidentiality

Ownership of the information contained herein belongs to Shanghai LianBio Development Co., Ltd. Confidential information is provided herein in accordance with the agreed and signed Disclosure and Nondisclosure Agreement. Without a prior written authorization, this document or its copy or any information contained herein cannot be disclosed to any third party (except those who conform to the Disclosure and Nondisclosure Agreement and coordinate the conduct of research work in the organization).

Version History

Version Number	Version Date	Major Amendments and Reason

Title	An Open-Label, Parallel-Group, Single-Center Phase 1 Clinical Study to Evaluate the Pharmacokinetics of a Single Oral Dose of Mavacamten in Healthy Adult Chinese Subjects					
Protocol No.	LB2001-101					
Sponsor	Shanghai LianBio Development Co., Ltd.					
Phase of Development	1					
Registration Category	Chemical Drug Category 1					
Proposed Indication	Obstructive Hypertrophic Cardiomyopathy (oHCM)					
	Name: Mavacamten Capsules					
Investigational	Strength: 10 mg and 15 mg					
Drug	Dosage form: capsules					
	Storage condition: $2\mathbb{C}$ to $25\mathbb{C}$ (36F to 77F)					
	Primary:					
	• To evaluate the pharmacokinetics (PK) of a single oral dose of mavacamten in					
	nearthy adult Chinese subjects with different CYP2C19 genotypes.					
Objectives	• To evaluate the safety and tolerability of a single oral dose of mayacamten in					
	healthy adult Chinese subjects with different CYP2C19 genotypes.					
	Exploratory:					
	• To evaluate the population PK.					
	PK endpoints include:					
	• Area under the curve (AUC) (0-last), AUC(0-inf);					
	• Maximum concentration (C _{max});					
PK Endpoints	• Time to maximum concentration (T _{max});					
	• Elimination half-life (T _{1/2});					
	• Apparent volume of distribution (V _d /F);					
	Apparent clearance (CL/F).					
	Safety endpoints include:					
	• Vital signs;					
Safety	Physical examination findings;					
Endpoints	Electrocardiogram (ECG) parameters;					
	• Clinical laboratory tests data, including hematology and blood chemistry, coagulation and urinalysis parameters:					
	 Adverse events (AEs). 					
Exploratory	 Population PK model may be assessed to investigate ethnic differences on key PK 					
Endpoint	parameters including clearance and volume of distribution.					
Sample Sizo	Approximately 44 healthy adult Chinese subjects are expected to be enrolled in this study according to CYP2C19 genotypes into 4 cohorts.					
Sample Size	• Cohort 1 and Cohort 2 (n = 12): ultra-rapid metabolizer (UM), rapid metabolizer (RM), or normal metabolizer (NM) of cytochrome P450 (CYP) 2C19 to ensure					

Synopsis

that data will be obtained for at least 10 subjects; Cohort 3 (n = 12): intermediate metabolizer (IM) of CYP2C19 to ensure that data • will be obtained for at least 10 subjects; Cohort 4 (n = 8): poor metabolizer (PM) of CYP2C19 to ensure that data will be obtained for at least 6 subjects. This is an open-label, parallel-group, single-center Phase 1 clinical study. Healthy adult Chinese subjects with different CYP2C19 genotypes (Cohort 1 and Cohort 2: CYP2C19 UM, RM, or NM; Cohort 3: CYP2C19 IM; Cohort 4: CYP2C19 PM) will be included and administered with a single oral dose of mavacamten to evaluate its PK profile. The doses administered include: 15 mg for cohort 1; 25 mg for Cohort 2; 15 mg for Cohort 3; 15 mg for Cohort 4. Blood samples will be collected from subjects at scheduled time points for PK testing. Series of safety assessments (including but not limited to AEs, laboratory tests, vital signs, and ECGs) will be performed during the whole study at specified time points. Pre-screening Screening In-house period Outpatient period EOS UM/NM/R M: Cohort 1:N=12 *17/*17 A single oral dose of 15 mg mavacamten will be administered and PK blood samples **Study Design** *1/*17 will be collected *1/*1 UM/NM/R CYP2C19 genotypes Cohort 2:N=12 End of study visit M: *17/*17 A single oral dose of 25 mg mavacamten will be administered and PK blood samples *1/*17 will be collected *1/*1 IM: Cohort 3:N=12 single oral dose of 15 mg mavacamten will be adm will be collected *1/*2 ed and PK blood samples *1/*3 PM Cohort 4:N=8 *2/*2 A single oral dose of 15 mg mavacamten will be administered and PK blood samples *3/*3 will be collected *2/*3 Up to 28 days Up to 13 days Subjects should return to the hospital for visits on Days 7, 10, 14, 21, 28, 35, 45 and 60 D75 D -43 D -15 D -1 D 3 Subjects can be enrolled in the study if they meet all of the following criteria: Male or female between the ages of 18 and 60 (inclusive) at screening (one sex 1 not less than 25% each cohort); Subjects who are CYP2C19 UM (*17/*17), CYP2C19 RM (*1/*17), CYP2C19 2. NM (*1/*1), CYP2C19 IM (*1/*2 or *1/*3) or CYP2C19 PM (*2/*2, *3/*3, or *2/*3) as per central laboratory phenotype interpretation during the pre-screening period; With a body mass index (BMI) between 18 kg/m² and 30 kg/m² (inclusive) at 3. screening; 4. With a resting left ventricular ejection fraction (LVEF) \geq 55% by Inclusion echocardiography at screening; Criteria 5. Healthy as determined by medical history, physical examination, vital signs, and laboratory tests (chemistry, hematology, coagulation and urinalysis), and 12-lead ECG at screening and on Day -1. Laboratory values outside the normal range are acceptable if such abnormalities are interpreted as being clinically insignificant. Screening assessments can be repeated for one more time at the investigator's discretion within the screening window;

6. Female subjects shall not be pregnant or breastfeeding and, if sexually active with male partner(s), must adopt one of the following highly effective contraceptive methods from the Screening Visit through 5 months after administration of the investigational medicinal product (IMP):

	• Estrogen and progesterone containing hormonal contraception associated with inhibition of ovulation or progesterone only hormonal contraception associated with inhibition of ovulation by oral, implantable, or injectable routes of administration;
	• Intrauterine device (IUD);
	• Intrauterine system (IUS);
	• Bilateral tubal ligation;
	• Females who have been surgically sterilized for more than 6 months or postmenopausal for more than 1 year. Permanent sterilization includes hysterectomy, bilateral oophorectomy, bilateral salpingectomy, and/or documented bilateral tubal ligation for at least 6 months prior to screening. Females are considered postmenopausal if they have had amenorrhea for at least 1 year or more following cessation of all exogenous hormonal treatments and their follicle stimulating hormone levels are in the postmenopausal range;
	7. Male partners of female subjects must also adopt a contraceptive method (e.g., barrier, condom or vasectomy) from screening through 5 months after administration of the investigational drug;
	8. Able to understand and comply with the study procedures, understand the risks involved in this study, and provide written informed consent according to local and institutional guidelines before screening procedure.
	Subjects must not be enrolled in the study if they meet any of the following criteria:
	 History of clinically significant arrhythmia, left ventricular (LV) systolic dysfunction, or coronary artery disease, or QTc >450 ms at screening and on Day -1;
	2. History of any type of malignant tumors, other than in situ cervical cancer or surgically excised non melanomatous skin cancers, within 5 years of the Screening Visit;
	3. Positive serologic tests at screening for infections with human immunodeficiency virus (HIV) antibody, hepatitis C virus (HCV) antibody or hepatitis B virus (HBV) surface antigen at screening;
Evolution	 4. Vital sign meet any of the following criteria: a) ear temperature was greater than 37.5 °C; b) heart rate was greater than 100 beats / min or less than 50 beats / min; c) systolic blood pressure was greater than 139 mmHg or less than 90 mmHg; d) diastolic blood pressure was greater than 90 mmHg or less than 50 mmHg at screening and on Day -1;
Exclusion Criteria	5. Subjects who have taken prescription medications within 28 days prior to screening or within 5 times of $T_{1/2}$ (if known), whichever is longer; or those who have taken over-the-counter medications (including herbal preparations and nutritional supplements) within 14 days prior to screening or within 5 times of $T_{1/2}$ (if known), whichever is longer (acetaminophen up to 1.5 g per day is allowed);
	6. History or evidence of any other clinically significant abnormalities, conditions, or diseases (with the exception of those outlined above) that, in the opinion of the investigator, would pose a risk to the safety of the subject or interfere with study evaluation, procedures, or its completion;
	7. Any condition or treatment for a condition that might interfere with the conduct of the trial or might, in the opinion of the investigator, put the subject at risk, including but not limited to, alcoholism, drug dependence or abuse, and psychiatric conditions, if he/she participates in this study;
	8. Positive test for alcohol or drug abuse at screening and on Day -1;
	9. Use of tobacco exceeding 10 cigarettes per day or nicotine-containing products

	of equivalent amount within 28 days prior to screening;					
	10. Hypersensitivity to mavacamten or any of the components of its formulation (Inactive ingredients are silicon dioxide, mannitol, hypromellose, croscarmellose sodium, and magnesium stearate (non-bovine). The capsule contains gelatin, titanium dioxide, black iron oxide, red iron oxide, and yellow iron oxide);					
	11. Prior exposure to mavacamten;					
	 Prior exposure to the investigational drug (or current use of an investigational device) within 30 days prior to screening, or at least 5 times of T_{1/2} (if known), whichever is longer; 					
	 Unable to comply with the study restrictions/requirements, including the number of required visits to the clinical site; 					
	14. Had donated over or lost 400 mL blood in 60 days or plasma in the last 2 weeks prior to the screening visit;					
	15. Infection of coronavirus disease 2019 (COVID-19) (i.e., positive for polymerase chain reaction) within 6 months prior to screening;					
	16. Unsuitable to participate in the study as judged by the investigator.					
	This study will consist of the following 5 periods:					
	• Pre-screening period (Day -43 to Day -15, up to 28 days)					
	Subjects who sign the pre-screening informed consent form (ICF) will enter the pre- screening period to determine their CYP2C19 genotypes.					
	• Screening period (Day-14 to Day -2, up to 13 days):					
	After determining their genotypes, subjects who sign the main ICF will enter the screening period to complete screening examinations.					
	• In-house period (Day -1 to Day 3, total 4 days):					
Study	Eligible subjects will be divided into 4 parallel cohorts based on their CYP2C genotypes (Cohort 1 and Cohort 2: CYP2C19 UM, RM, or NM; Cohort 3: CYP2C IM; Cohort 4: CYP2C19 PM).					
Procedures	Subjects will be admitted to the clinical research unit (CRU) the day before dosing (Day -1), and receive a single oral dose of mavacamten on Day 1 (Cohort 1: 15 mg; Cohort 2: 15 mg; Cohort 3: 15 mg; Cohort 4: 15 mg). They will remain in the CRU until Day 3 (48 hours after administration of mavacamten) for PK and safety assessments.					
	• Outpatient period (Day 4 to Day 75, total 72 days):					
	Subjects who have finished the examinations on Day 3 will enter the outpatient period. Outpatient visits will occur on Days 7, 10, 14, 21, 28, 35, 45 and 60 to collect blood samples and perform safety assessments.					
	• End of study visit (Day 75)					
	End of study (EOS) Visit will occur on Day 75 to complete the final safety examination and obtain the last blood samples for PK assessment.					
	Dosing Regimen					
	Subjects will receive a single dose of mavacamten on Day 1.					
	Cohort 1: 15 mg (15 mg capsules \times 1);					
Dosing Dosimon and	Cohort 2: 25 mg (10 mg capsules x 1 and 15 mg capsules x 1);					
Routes of	Cohort 3: 15 mg (15 mg capsules \times 1);					
Administratio	Cohort 4: 15 mg (15 mg capsules \times 1);					
n	Route of Administration					
	The drug is to be administered orally. Subjects should fast overnight (for at least 8 hours) before taking mavacamten with 240 mL water, and should not eat any food until 3 hours after dosing. Water will be allowed except for 1 hour before and after dosing.					

	PK Sampling Schedule							
PK Sampling	3 mL whole blood will be collected at each of the following time points for PK analysis: pre-dose (within 60 min before dosing), 10 min, 20 min, 30 min, 45 min, 1 h, 1.5 h, 2 h, 3 h, 4 h, 8 h, 12 h, 24 h and 48 h, and on Days 7, 10, 14, 21, 28, 35, 45, 60 and 75 after dosing of mavacamten.							
	Approximately 44 subjects will be enrolled in this study.							
	• Datasets							
	Pharmacokinetic Set (PKS):							
	All subjects exposed to mavacamten and with at least one plasma concentration will be included in the PKS.							
	Safety Analysis Set (SAS):							
	All subjects exposed to mavacamten, regardless of the doses administered, will be included in the SAS.							
	Statistical Analysis							
	PK Analyses:							
	Individual plasma concentration-time data of mavacamten will be displayed an summarized graphically on the linear and semi-log scales. PK parameters, includir AUC _(0-last) , AUC _(0-inf) , C _{max} , T _{max} , T _{1/2} , V _d /F, CL/F will be calculated using a non-compartmental model.							
Statistical	The concentration-time data for each cohort will be summarized and the mean concentration-time curve will be plotted on the linear and semi-log scales by cohort Descriptive statistical analysis for parameters will be performed by cohort.							
Methods	Statistics include the number of subjects, arithmetic mean, geometric mean (GM), standard deviation (SD), and coefficient of variation (CV), minimum (min), median, and maximum (max).							
	Safety Analyses:							
	Safety analyses will be based on descriptive statistics (summary tables) as well as individual data for AEs, clinical laboratory values, vital signs, and ECG parameters.							
	AEs will be coded using the Medical Dictionary for Regulatory Activities (MedDR AEs will be monitored throughout the study to determine their severity and t potential relationship to the investigational drug.							
	The number of subjects who experience AEs after dosing (from single dose administration to the EOS) will be summarized by cohort.							
	Population PK (PopPK) Analysis:							
	PopPK analysis will be conducted with the pooled data from the current study LB2001- 101 and other mavacamten studies. Additional details on PopPK model development and analysis will be provided in a separate PopPK data analysis plan (DAP), and the results of PopPK analysis will be reported in a separate clinical study report (CSR).							
	Note: PopPK analysis will be performed only after approval by relevant regulatory authorities and within the approved scope.							

Table 1 Study	Flow	Chart
---------------	------	-------

Weeks	Pre-screening	Screening Period	In-	house	Perio	d	Outpatient Period					End of study visit			
Days	D-43 to D-15	D-14 to D-2	D-1	D1	D2	D3	D7	D10	D14	D21	D28	D35	D45	D60	D75
Visit Window (day)							±1	±1	±1	±1	±1	±1	±1	±1	±1
Signing the pre-screening ICF ¹	Х														
Demographics ²	Х														
CYP2C19 genotyping	Х														
Signing the main ICF		Х													
Inclusion/exclusion criteria		Х	Х												
Assign subject number	Х	Х	Х												
Medical history		X													
Vital signs ³		X	Х	Х	Х	Х	Х	Х	Х	Х	Х	Х	Х	Х	Х
Physical examination ⁴		X	Х			Х									Х
Weight, height ⁵		Х													Х
12-lead ECG ⁶		Х	Х	Х		Х					Х			Х	Х
Echocardiography		X													
Hematology ⁷		X	Х								Х				Х
Blood chemistry ⁸		Х	Х			Х					Х				Х
Urinalysis ⁹		Х	Х								Х				Х
Coagulation ¹⁰		Х	Х			Х					Х				Х
FSH ¹¹		X													
Serum pregnancy test ¹²		X													Х
Urine Pregnancy test ¹²			Х								Х			Х	
Hepatitis B, C, and HIV virology		X													
Alcohol or drug abuse test ¹³		X	Х												
Investigational drug ¹⁴				Х											
PK blood sampling ¹⁵				Х	Х	Х	Х	X	Х	Х	X	Х	X	X	X
Concomitant medications		X	Х	Х	Х	Х	Х	Х	Х	Х	Х	Х	X	Х	X
AE ¹⁶	X	X	Х	Х	Х	Х	Х	Х	Х	Х	Х	Х	X	Х	Х

Abbreviations: AE = adverse event; ALP = alkaline phosphatase; ALT = alanine aminotransferase; APTT = activated partial thromboplastin time; AST = aspartate

aminotransferase; BP = blood pressure; CK = creatine kinase; CYP = cytochrome P450; ECG = electrocardiogram; EOS = end of study; FIB = fibrinogen; FSH = follicle stimulating hormone; HIV = human immunodeficiency virus; HR = heart rate; ICF = informed consent form; INR = international normalized ratio; PK = pharmacokinetic; PT = prothrombin time; QD = once daily; RBC = red blood cell; SAE = serious AE; TT = thrombin time; WBC = white blood cell.

Note: safety laboratory tests (hematology, blood chemistry, coagulation, urinalysis) are not required to be repeated on Day -1 if the latest results are within 7 days from Day -1. 12-lead ECG test is not required to be repeated on Day -1 if the latest result is within 3 days from Day -1.

1. Signing the pre-screening ICF: after signing of the pre-screening ICF, test for determining CYP2C19 genotypes could be performed.

2. Demographics: including age, gender and ethnicity.

3. Vital signs: including temperature, heart rate, respiratory rate, and systolic and diastolic BP in a supine position after 5 minutes of rest. While the subject is in the CRU, vital signs will be taken upon rising in the morning. On Day 1, vital signs should be collected before IMP dosing.

4. Physical examination: a complete physical examination will be conducted at screening and the EOS Visit, while abbreviated physical examinations on other visits. A complete physical examination includes assessments of general appearance, skin, head and neck, mouth, lymph nodes, thyroid, abdomen, and musculoskeletal, cardiovascular, neurological, and respiratory systems. Brief physical examination included cardiovascular and respiratory examinations.

5. Height, weight: weight (kg) will be measured at screening and the EOS Visit. And height (cm) will be measured at screening.

6. 12-lead ECG: it will be performed after 10 minutes of rest at screening, on Day -1, Day 1 (pre-dose: within 3h before dosing, and post-dose: 2 h±30min after dosing), Day 3, Day 28, Day 60, and at the EOS Visit. When the 12-lead ECG is completed, a 10-second paper ECG will be obtained as the subject's source documentation. If clinical symptoms or clinical indications occur accordingly, the investigator may consider increasing the frequency of test.

7. Hematology: including hematocrit, hemoglobin, RBC count, WBC count and differential, platelet count.

8. Blood chemistry: including albumin, total protein, direct bilirubin, total bilirubin, ALP, ALT, AST, creatinine, urea nitrogen, uric acid, CK, chlorine, potassium, sodium, calcium, magnesium, and glucose.

9. Urinalysis: including urine glucose, urine ketone bodies, urine pH, urine protein, urine specific gravity, urine leukocyte esterase, urine WBC and urine RBC.

10. Coagulation: including PT, INR, APTT, FIB, and TT.

11. FSH: FSH test will be performed at screening for postmenopausal women to confirm their postmenopausal status (serum pregnancy test at screening). If the result of FSH test shows that the subject is not postmenopausal, a pregnancy test (serum or urine) is required to be performed at another visit to ensure that the subject is not pregnant.

12. Pregnancy test: it will be performed in women of childbearing potential only. Serum pregnancy test will be performed at screening and the EOS Visit. Urine pregnancy test will be performed on Day -1, Day 28 and Day 60.

13. Alcohol or drug abuse test: a combination drug detection kit (colloidal gold method) will be used for this test to detect the amount of morphine, ketamine, tetrahydrocannabinic acid, methamphetamine, 3,4-Methylenedioxymethamphetamine and cocaine in human urine.

14. Investigational drug: administered orally on Day 1.

15. PK blood sampling: blood samples will be obtained at pre-dose (within 60 min before dosing), 10 min, 20 min, 30 min, 45 min, 1 h, 1.5 h, 2 h, 3 h, 4 h, 8 h, 12 h, 24 h and 48 h, and on Days 7, 10, 14, 21, 28, 35, 45, 60, and 75 after dosing of mavacamten to determine its plasma concentrations.

16. AEs: during the pre-screening and screening period, only study procedure -related AEs (e.g., blood sampling) will be collected.

Table 2 PK	Sampling	Schedule
------------	----------	----------

	In-he	ouse Period	I	Outpatient Period							End of study visit	
Days	D 1	D 2	D 3	D 7	D 7 D 10 D 14 D 21 D 28 D 35 D 45 D 60							D 75
Visit												
Window	0	0	0	±1	±1	±1	±1	±1	±1	±1	±1	±1
(day)												
Collection time points	Pre-dose (within 60 min before dosing) 10 min ± 2 min 20 min ± 2 min 30 min ± 2 min 45 min ± 2 min 1 h ± 2 min 1 h ± 2 min 2 h ± 3 min 2 h ± 3 min 3 h ± 3 min 4 h ± 3 min 8 h ± 5 min 12 h ± 5 min	24 h ± 1 h post-dose	48 h ± 1 h post-dose	Outpatient visits: 144 h ± 24 h post-dose on Day 1	Outpatient visits: 216 h ± 24 h post-dose on Day 1	Outpatient visits: 312 h ± 24 h post-dose on Day 1	Outpatient visits: 480 h ± 24 h post-dose on Day 1	Outpatient visits: 648 h ± 24 h post-dose on Day 1	Outpatient visits: 816 h ± 24 h post-dose on Day 1	Outpatient visits: 1056 h ± 24 h post- dose on Day 1	Outpatient visits: 1416 h ± 24 h post- dose on Day 1	EOS Visit: 1776 h ± 24 h post- dose on Day 1

TABLE OF CONTENTS

Clinical Study Protocol	1
Version History	1
Synopsis	1
TABLE OF CONTENTS	9
List of Tables	13
List of Appendices	13
List of Abbreviations	14
1. Introduction	16
 1.1 Background 1.2 Overview of Mavacamten 1.2.1 Basic Information 1.2.2 Clinical Experience with Mavacamten 1.3 Known and Potential Benefits and Risks 	16 17 17 17 18
2. Rationale for the Study and Administration	21
2.1 Rationale for the Study2.2 Rationale for Dose Selection	21 21
3. Objectives	22
4. Overall Study Design	23

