1.3 Known and Potential Benefits and Risks

There is no clinical benefit for the healthy subjects enrolled in the current study.

Based on nonclinical data and the available clinical data, four important risks have been described in the latest Development Safety Update Report with data lock point of 30-Oct-2020: heart failure due to systolic dysfunction defined as symptomatic LVEF < 50%, teratogenicity, QT prolongation, increased risk of heart failure due to interaction with CYP2C19 and potent CYP3A4 inhibitors.

> Heart failure due to systolic dysfunction defined as symptomatic LVEF < 50%

Data across nonclinical toxicology studies have shown that doses of mavacamten exceeding therapeutic levels can lead to reduced cardiac function, decreased blood pressure, compensatory increases in heart rate, and death. Clinical data has shown that dose-dependent, on-target reductions in LVEF have been monitorable with use of echocardiograms, reversible

with temporary or permanent discontinuation of treatment, and observed in the setting of mavacamten treatment alone or with concomitant conditions frequently observed in HCM, such as atrial fibrillation.

In patients with HCM, mavacamten's on-target mechanism of action reduces LVEF and may cause systolic dysfunction with LVEF < 50% with or without symptoms of left heart failure. Patients with a serious intercurrent illness or arrhythmia (e.g., atrial fibrillation or other uncontrolled tachyarrhythmia) may be at greater risk of systolic dysfunction. Data from MYK-461-006, conducted in subjects with nHCM, demonstrated that those who experienced decreases in LVEF returned to normal levels after interruption or discontinuation of study treatment. In the EXPLORER-HCM study (Study MYK-461-005), 7 subjects (5.7%) in the mavacamten group and 2 subjects (1.6%) in the placebo group experienced reversible reductions in LVEF < 50% while on treatment. In all 7 subjects treated with mavacamten, LVEF recovered following temporary interruption of dosing or was diagnosed at the end of the 30-week treatment period and recovered at Week 38. All subjects with an event of LVEF < 50% completed the study, with favorable changes from baseline in at least one key efficacy endpoint.

> Teratogenicity

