7.2 Safety Assessments

Safety will be assessed throughout the study (**Table 1**). Safety assessments include physical examinations, vital signs, ECGs, observed and subject-reported AEs, and safety laboratory results.

Any abnormal findings judged by the investigator to be clinically significant will be recorded as an AE (See Section 8.1).

Physical Examination

Physical examinations will be conducted at screening Day-1, Day 3 and at the EOS Visit. A complete physical examination will be conducted at screening and the EOS Visit. An abbreviated physical examination will be conducted on Days -1 and 3 (**Table 1**).

A complete physical examination includes assessments of general appearance, skin, head and neck, mouth, lymph nodes, thyroid, abdomen, and musculoskeletal, cardiovascular, neurological, and respiratory systems. Brief physical examination included cardiovascular and respiratory examinations.

Height (cm) and body weight (kg) will be measured at screening, and BMI (kg/m²) will be calculated. Body weight (kg) will be measured at EOS.

Vital Signs

Vital signs will be assessed at each study visit and include temperature, HR, respiratory rate, and systolic and diastolic BP in a supine position after 5 minutes of rest (**Table 1**). While the

subject is in the CRU, vital signs will be taken upon rising in the morning. On Day 1, vital signs should be collected within 3 h before IMP dosing.

12-lead ECG

Twelve-lead ECG evaluations will be performed after 10 minutes of rest in the supine position at screening, Day -1, Day 1 (pre-dose, within 3 h before dosing, and at 2 h \pm 30 min post-dose), Day 3, Day 28, Day 60 and the EOS Visit (**Table 1**). Parameters to be evaluated include, but are not limited to: HR, rhythm, PR interval, QRS interval, QT interval, P wave, QRS complex, T wave morphology, ST segment displacement, etc.

The investigator will judge the overall interpretation as normal or abnormal with clinical significance or abnormal with no clinical significance. The investigator will review the ECG with any other clinical findings, subject's medical history, and laboratory data to determine the clinical significance of the findings.

The investigator may add extra 12-lead ECG safety assessments if there are any clinically significant abnormal findings or if the investigator considers it is required for any other safety reason. These assessments should be recorded as an unscheduled assessment.

Other Safety Assessments

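### No blood pressure, respiratory rate or temperature reading is scheduled between dosing and the Day 2 morning, so the vital-signs summaries cannot describe blood pressure near peak concentration.

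*Protocol*

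**What the plan says.** Vital signs are a named safety endpoint (Protocol 10.2.2) and serve the secondary objective of safety and tolerability. They comprise temperature, heart rate, respiratory rate, and systolic and diastolic blood pressure, taken supine after 5 minutes of rest.

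- **Day 1.** Protocol Table 1 has one vital-signs entry for Day 1. Footnote 3 says "On Day 1, vital signs should be collected before IMP dosing". Section 7.2 says "On Day 1, vital signs should be collected within 3 h before IMP dosing". Neither gives a post-dose time.
- **Other in-house days.** "While the subject is in the CRU, vital signs will be taken upon rising in the morning" (footnote 3, repeated in section 7.2).
- **ECG.** A 12-lead ECG is scheduled on Day 1 before dosing and again afterwards ("post-dose: 2 h±30min after dosing"). On its content, section 7.2 says "Parameters to be evaluated include, but are not limited to: HR, rhythm, PR interval". Blood pressure is not an ECG parameter.
- **PK.** Protocol Table 2 schedules 11 post-dose samples on Day 1, from 10 min to 12 h.
- **Analysis.** Protocol 10.3.8.2 and SAP 4.9.4 summarise vital signs by time point with change from baseline. SAP 4.2 takes the last pre-treatment value as baseline, so Day 1 supplies only the baseline.

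**The concern.** Section 1.3 reports that, in nonclinical toxicology at doses above therapeutic levels, mavacamten can lead to "reduced cardiac function, decreased blood pressure, compensatory increases in heart rate, and death". Blood pressure is therefore a relevant signal for this drug. Echocardiography is scheduled only at screening, so after dosing the vital-signs row is the only scheduled source of blood pressure.

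The schedule follows concentration closely through the peak and places an ECG near it, but takes no blood pressure there. A finding of no change from baseline in vital signs would describe the Day 2 morning onwards. It could not be paired with any concentration from the first 12 h. That includes the interval in which Cohort 4 (PM, 15 mg) and Cohort 2 (UM/RM/NM, 25 mg) are expected to have their highest concentrations. An asymptomatic change in blood pressure in that interval would leave no scheduled record.

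**Working it through.** **1. When the first post-dose reading falls.** The Day 1 reading is within 3 h before dosing, and in-house readings are taken on rising. If subjects rise at about the same clock time on Day 2, that reading comes 24 h minus 0 to 3 h after dosing, that is, 21-24 h. The documents give no clock time for dosing, so this is an inference. Median Tmax in Protocol Table 3 is 0.75 h (PM), 1.0 h (15 mg IM) and 1.5 h (the other columns). The text of section 1.2.2 gives 0.5 h for MYK-461-011, which is earlier still. Scheduled blood-pressure readings after dosing and before the Day 2 morning: none, for any of the 44 planned subjects.

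**2. Check on the source figures.** Section 1.2.2 gives, for PM at 15 mg, AUC(0-inf) 42,800 h·ng/mL, T1/2 552.8 h, CL/F 350.5 mL/h and Vz/F 279,500 mL.

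- CL/F = Dose / AUC(0-inf) = 15,000,000 ng / 42,800 = 350.5 mL/h, as stated.
- Vz/F = CL/F × T1/2 / ln 2 = 350.5 × 552.8 / 0.6931 = 279,531 mL, against 279,500 stated.

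The published parameters are consistent with each other.

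**3. Concentration at 24 h as a share of Cmax.** The documents give no 24 h concentration, so it has to be approximated:

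C(24) ≈ [Dose / (Vz/F)] × 2^(−24 / T1/2), then divided by Cmax.

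Inputs are from Protocol Table 3.

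| Column | Dose / (Vz/F), ng/mL | T1/2, h | C(24), ng/mL | Cmax, ng/mL | C(24) / Cmax |
|---|---|---|---|---|---|
| 5 mg IM | 5,000,000 / 251,200 = 19.9 | 222.2 | 18.5 | 141.3 | 13.1% |
| 15 mg IM | 15,000,000 / 310,900 = 48.2 | 221.5 | 44.8 | 289.0 | 15.5% |
| 25 mg UM/RM/NM, Japanese | 25,000,000 / 306,800 = 81.5 | 153.8 | 73.1 | 504.0 | 14.5% |
| 25 mg UM/RM/NM, Caucasian | 25,000,000 / 276,600 = 90.4 | 155.7 | 81.2 | 515.8 | 15.7% |
| 15 mg PM | 15,000,000 / 282,300 = 53.1 | 571.6 | 51.6 | 489.0 | 10.6% |

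The PM values in the text of section 1.2.2 also give 10.6%.

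**4. Sensitivity.**

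- At 21 h instead of 24 h: 10.6-16.0%.
- Using λz × AUC(0-inf) in place of Dose / (Vz/F): 10.3-15.5%.
- Assigning part of the AUC to an early distribution phase, assumed to last 8-24 h: about 9-14.5%.
- If distribution were still incomplete at 24 h, the true share would be higher than the table shows. The documents do not allow this to be quantified.

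**The case against.** Several points count against making much of this.

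- **Other Day 1 safety data exist.** Adverse events are collected on Days 1 and 2 by open question, spontaneous report and observation (8.2.2), and subjects stay in the unit until 48 h. A symptomatic fall in blood pressure would be captured. Heart rate is recorded on the 2 h ECG. This stands, and it limits the gap to blood pressure, respiratory rate and temperature, chiefly where there are no symptoms.
- **Extra readings are allowed.** Sections 4.3.6 and 7 permit unscheduled or additional assessments at the investigator's discretion. True, but discretionary readings do not give a time point that can be summarised across subjects.
- **Most exposure comes later.** With a linear rise to Cmax at Tmax and a log-linear fall to the 24 h values above, AUC(0-24) is about 11% of AUC(0-inf) in PM (4,705 / 42,800), 20% in 15 mg IM (3,157 / 15,410) and 31% in 25 mg Japanese UM/RM/NM (5,399 / 17,370). Roughly 70-90% of exposure therefore follows 24 h, a period with 11 scheduled vital-signs readings. This stands: the schedule covers sustained exposure well. It does not cover the peak.
- **No acute effect is documented.** A reader might infer that the schedule misses the peak blood-pressure effect. The documents do not support that. The blood-pressure statement in section 1.3 is nonclinical and above therapeutic levels, and no time course is given. The nearest evidence concerns QTc: section 1.3 links prolongation in healthy volunteers to sustained exposure and reports no acute change in single-dose studies. The earlier single-dose studies in section 1.2.2 list only mild events and no hypotension, though their blood-pressure schedules are not given.
- **A 2 h reading is not at the peak.** The slot runs from 1.5 to 2.5 h, which is 0.75-1.75 h after median Tmax in PM and 0-1.0 h after it in the 25 mg columns. It is near-peak only.
- **The endpoint is secondary and descriptive**, and no passage claims coverage of the peak. This bears on priority, not on whether the gap exists.

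**Conclusion.** The gap is real and narrow. Two consistent passages place the only Day 1 vital signs before dosing, and nothing else schedules a blood pressure before the Day 2 morning. By then concentration is roughly 11-16% of Cmax. This rests on mono-exponential terminal decline by 24 h, on a mix of arithmetic-mean Vz/F and T1/2 with geometric-mean Cmax, and on Japanese, Caucasian and Asian subjects from earlier studies. Cohort 1 (UM/RM/NM at 15 mg) has no corresponding column. None of the alternatives that could be calculated puts the reading near peak.

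The supported conclusion is that the scheduled summaries cannot describe blood pressure, respiratory rate or temperature at or near peak concentration. It would go too far to say that they miss the peak effect, or that nothing is known about safety in the first 24 h. The primary PK analysis is unaffected. The point is worth acting on because the remedy is cheap and supports the secondary safety objective.

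**What to change.** In Protocol Table 1 footnote 3, Protocol 7.2 and the SAP 6.1 schedule, add one supine vital-signs reading on Day 1 in the existing 2 h (±30 min) post-dose ECG slot. Section 7 already prefers the order ECG, vital signs, then PK sample. The 10 minutes of supine rest for the ECG also covers the 5 minutes that vital signs require. In Protocol 10.3.8.2 and SAP 4.9.4, summarise the reading as its own time point with change from the pre-dose value, and describe it as near-peak rather than peak.

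Cost: a few minutes per subject (44 readings at planned enrolment), one eCRF row and one table row. No new visit, equipment or staff is needed.

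If dosing is already complete, state in Protocol 10.3.8.2 and SAP 4.9.4, and carry into the report, that scheduled vital signs do not cover about the first 24 h after dosing and cannot support a statement about blood pressure near peak concentration.
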